assumption that indeed, it may only be possible to determine an optimal RP2D in Part B of the study, as binding of NM21-1480 to PD-L1 is a pre-requisite for activation of the 4-1BB pathway by the compound. This is likely only possible in a tumor patient population with well-documented PD-L1 expression in the TME and since PD-L1 positivity was not an inclusion criterion for Part A, the likelihood of PD activity of the drug in Part A is reduced compared to Part B. In addition, in a situation with substantial excess of NM21-1480 over PD-L1 and 4-1BB on target cells in the tumor tissue, a decline in 4-1BB activity (due to a bell-shaped dose response curve for the 4-1BB agonistic activity of the compound) cannot be formally excluded to occur within the dose range explored in Part A of the study. Such bell-shaped dose response curve may occur because in such situation of substantial excess of NM21-1480, molecules over available PD-L1 and 4-1BB binding sites, an immediate saturation of PD-L1 and 4-1BB binding sites by different NM21-1480 molecules may occur. As such, concomitant binding of a single NM21-1480 molecule to both antigens may no longer be possible and consequently the immunological synapse between tumor cells and immune cells that is required to trigger 4-1BB signaling could no longer be established. This important aspect of dose finding was considered based on thorough review of the entirety of non-clinical and clinical data available at the end of the 28-day DLT evaluation period of the last patient enrolled to Part A. At this point (at the end of Part A SMC meeting on 23 May 2022), the SMC, together with the Sponsor, considered the nomination of up to 4 different dose levels of NM21-1480 and determine the optimal dosing interval (i.e., dosing approximately every 14 or 21 days) for administration of a given NM21-1480 dose for the optional Part A-2 and Part B with the goal to determine a final RP2D and dosing interval with an optimized activity and safety profile for future development within Part B. Part A study data discussed with SMC on 23 May 2022 demonstrated the development of treatment-emergent anti-drug-antibodies (ADAs) in a relevant fraction of patients dosed at 24mg-240mg. These ADAs were typically associated with rapid elimination of NM21-1480 from the circulation and loss of exposure. However, PK, PD, receptor occupancy and clinical activity data available for the 800mg dose level indicated that at this dose, the issue of loss of exposure was no longer present while full pharmacodynamic activity was maintained, a phenomenon described for other checkpoint inhibitors (i.e. atezolizumab) at higher doses as well. As such, the SMC agreed with the Sponsor to consider the 800mg dose to represent the presumptive RP2D and further study this dose, applying a biweekly dosing interval in Part B of the study. The SMC, together with the Sponsor, also considered at this point (i.e., at the end of the 28-day DLT evaluation period of the last patient enrolled to Part A) to enroll additional patients into an optional additional Cohort A-2 in parallel to Part B to complement the PK, immunogenicity and PD data to be provided by Part B. The Sponsor, following formal completion of Part A on 23 May 2022 is therefore exploring within this optional Cohort A-2 and under continuous review of emerging safety data by the SMC the safety, PK/PD and clinical activity profile of one higher dose level of NM21-1480 (1400mg flat dose) in up to 10 patients to complement Part B data and thus further inform development of NM21-1480 beyond initial Part B. As this dose level to be studied in Cohort A-2 is above the maximal dose level characterized in Part A, exploration of the 1400mg dose will be

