*Assessment of IPT, sPD-L1, sCD137, cytokine panel, RO, PD-L1 IHC, TMB, TCRseq, MSI and mRNA/IF may be adjusted for Part B, following availability of Part A data; conduct of RO assay (for Part A and B) will be dependent on availability of a suitable assay.

- a. Serial PK samples will be collected from all the patients enrolled in Part A and A-2. For the patients in Part B serial PK is optional except for the mandatory pre-dose, EOI and 168 ± 24 h sampling timepoints (see footnote "g").
- b. If a patient permanently discontinues study drug treatment, or is not receiving an infusion at a given visit, a single PK sample will be taken at that visit.
- c. Optional biopsy material for patients enrolled in Part A and A-2 from as many cycles as possible, and Follow-up period. For patients in Part B, a single post treatment biopsy material collection is considered mandatory per footnote "r" in [Table 7-1](#), i.e., for patients presenting with at least stable disease during treatment with NM21-1480.
- d. Optional sampling point for Part B. Sites are not required to collect these optional PK samples in Part B. These sampling timepoints are however mandatory in Part A and Part A-2. For sampling timepoints considered mandatory in Part B at all sites, see also footnote "g".
- e. EOI: End of Infusion. This sample should be taken immediately prior to stopping the infusion from the counter arm of the site of injection. All subsequent timepoints indicated for PK blood draws refer to hours *after* EOI.
- f. For FU visits: PK and ADA sample will be taken at Follow-up Visit 1 only.
- g. Mandatory sample for all patients in Part A, Part A-2 and Part B (unless drawing is not considered clinically feasible due to the condition of the patient).
- h. Only applicable for mCRC patients enrolled to Cohort B8. For specifics on sample acquisition please refer to specialty lab manual.
- i. Reference is made to footnote gg in Table 7-1 for timing of these mandatory on-treatment biopsies for mCRC patients enrolled to Cohort B8.
- j. Not applicable to patients in Cohort B5 randomized to standard-of-care anti-PD1 therapy only.
- k. Only applicable for mCRC patients enrolled to Cohort B8.

Table 7-4 Backup Pharmacokinetics, Anti-Drug Antibody, and Pharmacodynamic Blood Sampling Schedule (3-week Dosing Interval: APPLICABLE TO PART A-2 AND B ONLY IN CASE OF A POTENTIAL FUTURE SMC DECISION TO PROLONG DOSING INTERVAL#)

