3.5.1 Sample Collections for Pharmacokinetic Analysis

Pharmacokinetic blood sampling timepoints for determination of serum concentrations of NM21-1480 (2-week Dosing Interval) during Part A, Part A-2 and Part B of the study

VISIT	DAY	PK SAMPLING TIME
Cycle 1	1	(Pre-dose) 0 EOI ± 5 min [#] 4 h ± 10 min* 8 h ± 1 h*
	2	24 h ± 2 h*
	3	48 h ± 4 h*
	5	96 h ± 12 h*
	8	168 h ± 24 h
	15 ± 2	(Pre-dose) 0
Cycle 2	1 ± 2	(Pre-dose) 0
	8 ± 2	168 h ± 48 h
	15 ± 2	(Pre-dose) 0
Cycle 3	1 ± 3	(Pre-dose) 0 EOI ± 5 min [#] 4 h ± 10 min*

		8 h ± 1 h*
2		24 h ± 2 h*
3		48 h ± 4 h*
5		96 h ± 12 h*
8		168 h ± 24 h
15 ± 3		336 h ± 48 h*
Every subsequent even cycle	8 ± 3	168 h ± 48 h
Every subsequent odd cycle	1 ± 3	(Pre-dose) 0
First follow up visit		Anytime

* EOI: End of Infusion sample is taken immediately prior to stopping the infusion from the counter arm of the site of injection. All subsequent timepoints indicated for PK blood draws refer to hours *after* EOI

* Optional sampling point for Part B. Sites are not required to collect these optional PK samples in Part B. These sampling timepoints are however mandatory in Part A-2

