3.5.2 Handling Missing or Below the Lower Limit of Quantification Data

For PK concentration data, if the actual sampling time is missing, but a valid concentration value has been measured, the concentration value will be flagged, and the scheduled nominal time point may be used for the calculation of PK parameters.

In cases of missing pre-dose concentrations prior to the first dose of Cycle 1, the missing concentration value may be imputed as zero. If missing pre-dose concentrations of Cycle 3, the pre-dose of Cycle 4 (or any cycle after Cycle 3) may be used as pre-dose concentration values. For the other cases, the missing data will not be imputed.

For the individual concentration and PK parameter calculation for Part A and A-2 by dose level and cycle and Part B by cohort and cycle, the following rules will be applied:

- If one or more below the limit of quantitation (BLQ) values occur before the first measurable concentration, they will be assigned a value of zero.
- If BLQ values occur between measurable concentrations in a profile, the BLQ should be omitted (set to missing).
- If BLQ values occur after the last measurable concentration in a profile, the BLQ should be omitted (set to missing).

For the concentration summary of NM21-1480 and mean (±SD) concentration plot preparation for Part A and A-2 by dose level and cycle and Part B by cohort and cycle, the following rules will be applied:

- Mean concentration at any individual time point will only be calculated if at least half of the patients have valid values (i.e. quantifiable and not missing) at this time point for each dose level, cohort and cycle.
- In cases where a mean value is not calculated due to the above criterion not being met, the value will be set to missing.
- BLQ values will be set to zero.
- The value of zero will be excluded from the calculation of GM and GM CV%

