3.5.4 Pharmacokinetics Parameters

The following serum PK parameters of NM21-1480 will be determined using WinNonlin v8.3 non-compartmental methods as appropriate for all parts (A, A-2 and B) for all patients for whom parameters can be calculated:

Parameters	Description and Calculation	Cycle
C_{max}	Maximum serum concentration; determined directly from the concentration time profile; if the maximum serum concentration occurs at more than one time point, C_{max} is defined as the first maximum value	Cycle 1, Cycle 3

C_{min}	Minimum serum concentration over the dosing interval	Cycle 1, Cycle 3
T_{max}	Time to C_{max} ; If the maximum value occurs at more than one time point, T_{max} is defined as the first time point with this value	Cycle 1, Cycle 3
λ_z	Apparent first-order terminal elimination rate constant calculated from a semi-log plot of the serum concentration versus time curve. The parameter will be calculated by linear least-squares regression analysis using points in the terminal log-linear phase.	Cycle 1, Cycle 3
$t_{1/2}$	Apparent first-order terminal elimination half-life; calculated as $\ln(2)/\lambda_z$	Cycle 1, Cycle 3
AUC_{0-t}	Area under the serum concentration vs time curve (AUC) from predose (time 0) to the last quantifiable serum concentration (C_{last})	Cycle 1, Cycle 3
AUC_{tau}	AUC over the dosing interval	Cycle 1, Cycle 3
AUC_{0-inf}	AUC from time 0 to infinity; calculated as $(AUC_{0-t} + C_{last}/\lambda_z)$	Cycle 1
$AUC_{%extrap}$	Percent of AUC_{0-inf} extrapolated, represented as $(1 - AUC_{0-t}/AUC_{inf}) * 100$	Cycle 1, Cycle 3
CL	Total serum clearance after IV administration; calculated as Dose/ AUC_{inf}	Cycle 1
CL _{ss}	Total serum clearance after IV administration; calculated as Dose/ AUC_{tau}	Cycle 3
Vd	Volume of distribution during terminal elimination phase after IV administration; calculated as Dose/ $[\lambda_z * AUC_{inf}]$	Cycle 1
Vd _{ss}	Volume of distribution during terminal elimination phase after IV administration; calculated as Dose/ $[\lambda_z * AUC_{tau}]$	Cycle 3
Accumulation Index (AR _{Cmax})	Accumulation ratios assessment of C_{max} ; calculated as C_{max} in Cycle 3 divided by C_{max} in Cycle 1	Cycle 3

Accumulation Index (AR _{C_{min}})	Accumulation ratios assessment of C _{min} ; calculated as C _{min} in Cycle 3 divided by C _{min} in Cycle 1	Cycle 3

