Accumulation Index (AR _{AUC})	Accumulation ratios assessment of AUC; calculated as AUC _{tau} in Cycle 3 divided by AUC _{tau} in Cycle 1	Cycle 3

Actual collection times will be used in PK parameter calculations. The Linear-Log Trapezoidal method (equivalent to the Linear Up/Log Down option in WinNonlin) will be used in the computation of all AUC values. In order to estimate the apparent first-order terminal elimination constant, λ_z , linear regression of concentration in logarithm scale vs. time will be performed using at least 3 data points post C_{max}. Uniform weighting will be selected to perform the regression analysis to estimate λ_z . The constant λ_z will not be assigned if one of the following occurs:

1. The terminal elimination phase is not linear (as it appears on a semi-logarithmic scale).
2. The terminal elimination rate constant indicates a positive slope ($\lambda_z > 0$).
3. T_{max} is one of the three last data points.

The constant λ_z and its derived parameters will be flagged and included in the statistical analysis if one of the following occurs:

1. The adjusted regression coefficient (R²) is less than 0.8.
2. The AUC_{%extrap} exceeds 20%.

No value for λ_z , AUC_{0-inf}, AUC_{%extrap}, CL, CLss, Vz, Vzss or t_{1/2} will be reported for cases that do not exhibit an acceptable terminal log-linear phase in the concentration-time profile.

No PK parameters will be calculated for patients with 2 or fewer detectable concentrations in their PK profile.

PK parameters will be listed per patient and summarized by dose level and cycle (combined for Part A and A-2) and by cohort and cycle (Part B). The summaries of PK parameters will use following descriptive statistics: n, arithmetic mean, standard deviation, geometric mean, geometric standard deviation, 95% CI geometric mean, coefficient of variation (CV%), geometric CV% (calculated as: gCV% = $\sqrt{e^{s^2}-1} * 100$; where s is the standard deviation of the log-transformed values), minimum, maximum and median. Tmax will include median, minimum and maximum. No descriptive statistics will be determined when fewer than three individual PK parameters are available.

All available data will be presented in patient data listings which will be sorted by patient and visit date as applicable.

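### SAP 3.5.4's three-value minimum drops Cmax, Tmax and Cmin for a Part B patient with mandatory sampling only as soon as one sample is BLQ, which tilts those tables towards patients who kept exposure

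*SAP*

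**What the plan says.** **Minimum-data rule.** SAP 3.5.4: "No PK parameters will be calculated for patients with 2 or fewer detectable concentrations in their PK profile". No parameter is exempt. The same section separately asks for at least three points after Cmax before lambda-z is estimated, and withholds half-life, AUC to infinity, clearance and volume where the terminal phase is unacceptable. Cmax and Tmax are read from the observed profile, and Cmin is the "Minimum serum concentration over the dosing interval". Accumulation ratios divide Cycle 3 by Cycle 1. No descriptive statistics are given when fewer than three individual values are available.

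**Sampling.** Protocol Table 7-3, footnote a: "For the patients in Part B serial PK is optional except for the mandatory pre-dose, EOI and 168 ± 24 h sampling timepoints". SAP 3.5.1 agrees. It stars the Cycle 3 samples at 4, 8, 24, 48, 96 and 336 h, with the note "Optional sampling point for Part B. Sites are not required to collect these optional PK samples in Part B".

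**BLQ handling for parameters.** In SAP 3.5.2, when BLQ "values occur before the first measurable concentration, they will be assigned a value of zero". BLQ values after the last measurable one are omitted. A later cycle can stand in for an absent value: "If missing pre-dose concentrations of Cycle 3, the pre-dose of Cycle 4 (or any cycle after Cycle 3) may be used". Nothing similar is offered for a BLQ pre-dose value.

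**Why BLQ matters here.** Protocol 7.1, on Part A patients dosed at 24 to 240 mg: "These ADAs were typically associated with rapid elimination of NM21-1480 from the circulation and loss of exposure". Protocol 7.2.5 reports that this was not seen at 800 mg, the Part B dose.

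**The concern.** Three quantifiable points are needed for a terminal slope. They are not needed to read a maximum or a trough. Because lambda-z already has its own, stricter requirement, a profile with two detectable values fails it anyway. The general rule therefore adds only the loss of Cmax, Tmax, Cmin and any interval AUC.

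That loss is unlikely to be random. A BLQ value before a dose or at 168 h is how rapid ADA-driven elimination would show itself. PK parameters are secondary endpoints in every part. Part B, with 20 patients (SAP 6), is the main further source of 800 mg data. The protocol's own benefit-risk text (5.3.3) asks for continued attention to the effect of ADAs on long-term exposure. A Cmin table that loses some of the patients with the lowest troughs is a poor answer to that request.

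**Working it through.** The plan gives no figure to reproduce. The check is a count of samples, followed by illustrations under stated assumptions.

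**Step 1. Samples per cycle (SAP 3.5.1, Protocol Table 7-3).**

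| Cycle | Scheduled | Mandatory in Part B |
|---|---|---|
| 1 | 9 | 4: pre-dose, EOI, 168 h, Day 15 pre-dose |
| 3 | 9 | 3: pre-dose, EOI, 168 h |

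**Step 2. Apply the rule, reading a profile as one cycle.** SAP 3.5.2 uses the word in a passage organised by cycle, but does not define it.

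- Cycle 3, mandatory samples only: 3 − 0 BLQ = 3 detectable, so parameters are computed. 3 − 1 = 2 detectable, so none are. The margin is zero.
- Cycle 1, mandatory samples only: the sample before the first dose should be BLQ, so 4 − 1 = 3 remain. A BLQ value at 168 h or at Day 15 pre-dose leaves 2, so none are computed.
- Losing either cycle also loses the Cmax and Cmin ratios.
- Full schedule (Parts A and A-2): 9 − 3 = 6 BLQ values are tolerated in Cycle 3.
- A Part B patient with one further quantifiable optional sample survives one BLQ value.

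**Step 3. AUC.** With mandatory Cycle 3 samples only, one point (168 h) follows EOI. Lambda-z cannot be estimated whatever the BLQ status, and AUC over the 14-day interval is probably unavailable too. The rule does not drive the AUC ratio.

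**Step 4. Illustrative effect on mean Cmin.** Let q be the share of a cohort removed, m the mean Cmin of those kept, and count BLQ as 0. The mean over all patients is (1 − q)m, and the table shows m. Overstatement = 1/(1 − q) − 1.

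| q | Example | Overstatement |
|---|---|---|
| 0.1 | 1 of 10 | 11% |
| 0.2 | 1 of 5 | 25% |
| 0.3 | 3 of 10 | 43% |
| 0.4 | 2 of 5 | 67% |

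**Step 5. Chance that a cohort summary disappears.** SAP 6 gives 5 patients in each of B1 and B7, and 10 in B8. Assume all reach Cycle 3 with mandatory sampling only. The number kept is binomial(n, 1 − q), and the summary is lost when fewer than 3 are kept. For n = 5 and q = 0.2: 0.00032 + 0.0064 + 0.0512 = 5.8%.

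| q | n = 5 | n = 10 |
|---|---|---|
| 0.1 | 0.9% | <0.1% |
| 0.2 | 5.8% | <0.1% |
| 0.3 | 16.3% | 0.2% |
| 0.4 | 31.7% | 1.2% |
| 0.5 | 50.0% | 5.5% |

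**Step 6. What Part A says about q.** Protocol Table 10-5 has 9 DLT-evaluable patients at 800 mg. If the report of no loss of exposure means 0 of 9 (an assumption), the two-sided 95% upper limit is 1 − 0.025^(1/9) = 33.6%. Part A supports a low rate but does not exclude a substantial one.

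**The case against.** The strongest reply is that the information is not lost. SAP 3.5.3 summarises concentrations at each nominal time by cohort and cycle, lists every value, and plots mean and individual 168 h and trough concentrations. SAP 3.5.2 sets BLQ to zero in those summaries and gives a mean when at least half the patients have quantifiable values. At any q from 0.1 to 0.4, and with no missing samples, the arithmetic mean trough including the affected patients is produced. The EOI value, which would be Cmax, is also listed and summarised. The patients remain in the PK Set. All of this stands. It does not correct the parameter tables, though, and zeros are left out of the geometric means.

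A reader might infer that the rule removes exactly the patients who lost exposure. The documents do not support that. Low but quantifiable troughs stay in, and so do Part B patients with enough optional samples. A sample that was not drawn, which Table 7-3 footnote g allows when drawing it is not clinically feasible, can trigger the same exclusion.

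Nor do the documents give a basis for any particular q. They report no loss of exposure at 800 mg in Part A. The one timed ADA case they describe (Protocol 5.2) followed four months of treatment at 24 mg, later than Cycle 3 Day 1 (Day 57).

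Finally, PK output is descriptive, no PK/PD analysis is planned, and the trial closed early. That limits the weight of the point but does not remove it.

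**Conclusion.** The point holds, within limits. For Part B patients with mandatory sampling only, one BLQ value in Cycle 3, or at 168 h or Day 15 pre-dose in Cycle 1, removes Cmax, Tmax and Cmin for that cycle and the Cmax and Cmin accumulation ratios. Because BLQ is expected where ADAs speed elimination, the Part B Cmax and Cmin tables would tend to over-represent patients who kept exposure.

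This rests on reading a profile as one cycle's profile. The size is unknown: the 11% to 67% range depends on assumed values of q and on counting BLQ as zero.

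Three broader conclusions are not supported: that Parts A and A-2 are affected in the same way by one BLQ value, that AUC-based accumulation is biased by this rule, or that loss of exposure is hidden from the report. This is a cheap improvement to secondary-endpoint tables, not a threat to the trial's conclusions.

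**What to change.** 1. In SAP 3.5.4, define a profile as one cycle's samples, and limit the three-value minimum to lambda-z and the parameters that depend on it.
2. Report Cmax and Tmax whenever an EOI sample exists, and Cmin whenever the relevant trough sample exists. Name that sample for each cycle. In Cycle 1 use the post-dose trough (Day 15 pre-dose), not the zero before the first dose. In Cycle 3 the Day 1 pre-dose sample is the only mandatory trough in Part B, since 336 h is optional.
3. Amend SAP 3.5.2 so that a BLQ trough is kept for Cmin, as 0 or as below LLOQ. Changing 3.5.4 alone would leave the two sections in conflict, because a trailing BLQ value would still be omitted.
4. Show the number of patients with a BLQ trough by cohort and cycle.

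The cost is SAP wording and table programming; no new samples are needed. Geometric means cannot include zeros, so the BLQ count must stand beside them. A Cmin ratio with a zero Cycle 1 denominator cannot be formed, and such patients should be counted too.

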3.5.5 Pharmacokinetic/Pharmacodynamic Analysis

No PK/PD relationship analysis will be provided.

3.5.6 Pharmacodynamic Assessment

No pharmacodynamic analysis will be performed.

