10.3.2 Part A-2 (Optional): PD Expansion

The primary objective of the optional Part A-2 is to better understand the exposure-dependent PD/dose response relationship. PD data will be combined across Part A and Part A-2 and summarized using descriptive statistics. If appropriate, the PD/dose relationship may be modelled. The shape of the dose response curve will be identified after plotting the data.

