2.2 Study Objectives – Part A-2

2.2.1 *Primary Objectives*

- To assess the safety and tolerability of NM21-1480 at a dose level beyond what has been assessed in Part A (i.e. at 1400mg)
- To further explore drug-exposure/PK/PD relationships in order to complement respective Part B data when conducted in parallel to Part B

2.2.2 *Secondary Objectives*

- To characterize the PK profile of NM21-1480
- To evaluate the immunogenicity of NM21-1480

2.2.3 *Exploratory Objectives*

- To determine the anti-tumor activity of NM21-1480 according to RECIST1.1

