Part A-2 was an optional part of the study. It was initiated after determination of the MTD based on Part A data. On 23 May 2022, the SMC determined that Part A did not technically identify a MTD and the highest dose level assessed (800mg) was considered a tolerated dose. The rationale behind the potential conduction of Part A-2 was to cover situations in which the SMC, together with the Sponsor, upon comprehensive review of all available data at the time of MTD determination (i.e. at the formal end of Part A on 23 May 2022), came to the conclusion that either additional exposure-dependent PD data at dose levels at or below the MTD were needed to allow for selection of the up to 4 dose levels to be further studied in Part B, or it may be desirable to explore different dose levels and/or dosing intervals in parallel to Part B to complement the PK, immunogenicity, and PD data to be provided by Part B to inform development of NM21-1480 beyond Part B. Based on the finding that some patients dosed at 24-240mg in Part A developed treatment-emergent ADAs leading to loss of exposure, while this was not observed at the 800mg dose level, a decision was taken to explore one additional higher dose level (1400mg flat dose) in up to 10 patients within Part A-2 in parallel to studying the 800mg dose level in Part B. The primary intention of exploring this 1400mg dose level in Part A-2 was to further characterize the overall PK/PD relationship of NM21-1480 over a broad range of doses. Patients enrolled into this optional cohort needed to fulfill Part A eligibility criteria but in addition will needed have documented minimal PD-L1 expression on at least 1% of tumor and/or immune cells in the TME, as detected by local testing with a Food and Drug Administration (FDA)-cleared or any PD-L1 assay approved for use by local competent authority. As the 1400mg flat dose level explored in Part A-2 was above the maximal dose level characterized in Part A, exploration of the 1400mg dose level was conducted under the continuous safety data review and guidance by the SMC. In this setting in which Part A-2 was conducted in parallel to Part B, its resulting data was used to complement Part B data in regards of getting to a comprehensive understanding on the PK/PD relationship of different dosing regimens for NM21-1480 before engaging into subsequent clinical development steps beyond Part B.

Part B

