2.7 Study Endpoints – Part A-2

2.7.1 *Primary Endpoints*

- Incidence and severity of TEAEs with specific focus on incidence and severity of irAEs
- Characterization of exposure-dependent PD markers of target and pathway engagement. Potential PD markers are included in the below list of exploratory markers applicable to all Parts A, A-2, and B

2.7.2 *Secondary Endpoints*

- PK parameters
 - AUC_{tau}
 - AUC_{0-inf} (first dose only)
 - AUC_{0-t}
 - C_{max}
 - C_{min}
 - $t_{1/2}$
 - T_{max}
 - λz
 - CL
 - CL_{ss}
 - V_d
 - V_d_{ss}
- Frequency of specific anti-drug antibodies to NM21-1480

2.7.3 *Exploratory Endpoints*

- BOR
- ORR
- TTR
- DOR
- PFS
- OS

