4 SAFETY MONITORING COMMITTEE AND DATA MONITORING COMMITTEE

A Safety Monitoring Committee (SMC) monitored and reviewed accumulating data to detect potential risks to enrolled patients. The SMC evaluated delayed DLTs, reviewed ad-hoc safety issues, and supported the Sponsor in MTD determination. They were also planned to support the interim futility decisions for the Part B cohorts. The SMC consisted of an independent (i.e. not an investigator in the study) Chair and site investigators. Full details on SMC membership responsibilities are found in the SMC charter.

The SMC together with the Sponsor selected the dose levels and dosing intervals for Part B of the trial. A Data Monitoring Committee (DMC) was planned to review the accumulating clinical activity, PK/PD, ADA, and RO data, but was not needed due to early closure of the trial.

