6 CHANGES FROM PROTOCOL-SPECIFIED STATISTICAL ANALYSIS

Only limited patients were enrolled onto the study under Cohort B1 (5 patients), Cohort B7 (5 patients) and Cohort B8 (10 patients) in Part B. Cohort A-2 only enrolled 5 patients. There are no patients enrolled under Cohort B2, Cohort B3, Cohort B4, Cohort B5 and Cohort B6 in Part B. Therefore, due to the limited data, only related TFLs will be generated and no interim analyses were performed.

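### The SAP cancels all PD and PK/PD analysis while still listing PD as a primary endpoint of Parts A-2 and B and PK/PD as a primary objective of Part A-2

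*SAP*

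**What the plan says.** SAP 3.5.5 and 3.5.6 are one sentence each: "No PK/PD relationship analysis will be provided" and "No pharmacodynamic analysis will be performed". Neither gives a reason or is limited to one part of the study.

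The same SAP keeps PD at the top of its hierarchy:

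- Section 2.2.1, primary objective of Part A-2: "To further explore drug-exposure/PK/PD relationships in order to complement respective Part B data".
- Section 2.7.1, primary endpoint of Part A-2: "Characterization of exposure-dependent PD markers of target and pathway engagement". Section 2.8.1 lists the same endpoint as primary for Part B.
- Section 2.5.1, on why the dose was studied: "The primary intention of exploring this 1400mg dose level in Part A-2 was to further characterize the overall PK/PD relationship of NM21-1480".

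Protocol 10.3.2 plans a descriptive analysis: "PD data will be combined across Part A and Part A-2 and summarized using descriptive statistics". Protocol 10.6.11 adds tabulation of PD markers by cycle, visit and dose. Modelling of PD against dose was only an option in the protocol.

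Two SAP passages come near an explanation. Section 6 gives the low enrolment and concludes "due to the limited data, only related TFLs will be generated and no interim analyses were performed". Section 4 says that the Data Monitoring Committee "was planned to review the accumulating clinical activity, PK/PD, ADA, and RO data, but was not needed due to early closure of the trial".

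**The concern.** A primary endpoint with no analysis means that the final report cannot answer a question the plan still declares primary. The five patients given 1400 mg were enrolled mainly to inform the PK/PD relationship, and that relationship would not be addressed. PD activity was also part of the case for taking 800 mg into Part B (protocol synopsis, Part A; protocol 5.1.3), but the final analysis would hold no PD summary to show it. For Parts A-2 and B, a reader could not tell whether PD was never assayed, was unusable, or was left out.

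**Working it through.** The plan gives no figure to reproduce. The check compares passages and adds counts.

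**1. Patients for whom PD is primary.** SAP section 6 gives the enrolment: A-2 5, B1 5, B7 5, B8 10.

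- PD as a primary endpoint (A-2 and Part B): 5 + 5 + 5 + 10 = 25 patients.
- PK/PD as a primary objective (A-2 only): 5 patients.

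**2. Do the stated reasons cover the removal?** Section 6 refers to A-2 and Part B enrolment and does not name PD or PK/PD. Section 4 explains why a committee review was not needed. Neither reason reaches Part A, which SAP 3.5.6 also covers. Protocol Table 10-5 shows 1 + 1 + 3 + 3 + 5 + 3 + 9 = 25 evaluable patients there, the planned maximum.

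**3. Do small groups explain it?** The SAP keeps the following for the same groups:

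| Data | SAP section | Kept? |
|---|---|---|
| PK parameters, with no descriptive statistics below three values and listings retained | 3.5.4 | Yes |
| Anti-drug antibodies | 3.5.7 | Yes |
| BOR and ORR | 3.4.2.1, 3.4.2.2 | Yes |
| Kaplan-Meier PFS and OS | 3.4.2.3, 3.4.2.4 | Yes |
| PD and PK/PD | 3.5.5, 3.5.6 | No |

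If Kaplan-Meier quartiles are planned for cohorts of 5, small numbers alone do not rule out a listing or simple summary of PD.

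**4. Are there PD data?**

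- *Part A:* yes. PD results are cited at 80 mg (protocol 10.3.1; 5 evaluable patients) and at 800 mg (synopsis; 9 evaluable), which gives 5 + 9 = 14 of 25 evaluable patients at those two doses. Protocol 5.3.1 uses PD data to define the relevant range of 24 to 800 mg, which holds 3 + 5 + 3 + 9 = 20 of 25. These are DLT-evaluable counts by dose. The number of patients with a PD result is not given.
- *Parts A-2 and B:* unknown. Protocol Table 7-3 marks cytokine and soluble-marker samples in Cycle 1 as mandatory in every part at Day 1 pre-dose, end of infusion, Day 8 and Day 15. That is 1 baseline and 3 post-dose samples per patient. The table also allows PD assessments to be adjusted for Part B, and nothing says how many samples were assayed. Coverage is therefore between 0 and 25 patients.

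**5. Can the SAP drop this on its own authority?** Protocol 10.1 lets the SAP modify methods, but requires a major modification of a primary endpoint's analysis to be described in a protocol amendment as well. Removing the analysis entirely is major. The supplied protocol describes no such removal, and whether a later amendment does cannot be settled from these documents.

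**6. A smaller, separate gap.** Comparing SAP 2.8.2 with 3.4, four secondary items have no analysis: time to response, duration of response by RECIST 1.1, duration of response by iRECIST, and PFS by iRECIST. Disease control rate is not counted, because it can be read from the BOR table.

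**The case against.** The strongest reply is that the evidence of data and the primary status belong to different patients. Every passage reporting PD results concerns Part A, where PD is exploratory (SAP 2.6.3), so the amendment rule does not apply there. Where PD is primary, the documents do not show that any sample was assayed. Receptor occupancy depended on a suitable assay, and mandatory draws could be skipped if clinically infeasible. PD is thus not fully comparable with PK or anti-drug antibodies. This stands, and it is why the number affected is given as a range.

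It can also be said that protocol 5.1.3 bases the choice of 800 mg primarily on anti-drug antibodies with loss of exposure at lower doses, and the SAP still analyses antibodies and PK. That also stands: PD was a supporting part of the rationale, not its core. The full marker list in SAP 2.9.1 is long, so restoring everything could take more than a few tables.

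Finally, section 6 does give a reason of a kind, and the omission is stated openly. But that reason never names PD and cannot account for Part A. None of these points removes the conflict between the declared primary endpoint and its cancelled analysis.

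**Conclusion.** The concern holds and should be fixed. The SAP declares PD a primary endpoint for 25 patients and PK/PD a primary objective for 5 of them, then provides no analysis of either and no PD-specific reason. That inconsistency rests on the text alone and needs no assumption. How much reportable information is lost does depend on an unknown: between 0 and 25 patients in A-2 and Part B, and some number above zero in Part A. The safety and BOR primaries are still analysed and SAP 3.1.5 excludes hypothesis testing, so type I error and power are unaffected. Losing the optional modelling breaks no commitment. Losing the descriptive summaries departs from protocol 10.3.2 and 10.6.11.

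**What to change.** Replace SAP 3.5.5 and 3.5.6 with descriptive change-from-baseline summaries of whatever PD was assayed, or listings where values are few. Present them by dose and visit for Parts A and A-2 combined and by cohort for Part B, shown alongside exposure. The sparse-data rule already used for PK could be adopted. No modelling is needed.

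Where PD cannot be analysed, section 6 should name the removal and give its reason. Sections 2.2.1, 2.7.1 and 2.8.1 should be aligned with it, and the SAP should state that the A-2 PK/PD objective is not addressed. The sponsor should confirm whether the amendment required by protocol 10.1 exists. For time to response, duration of response (both criteria) and iRECIST PFS, either add the analysis (protocol 10.6.2.4 already defines duration of response) or declare them dropped in section 6.

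No new patients or procedures are needed. For Part A the cost is descriptive tables or listings, with the number depending on how many markers are reported. For A-2 and Part B it is similar work if samples were assayed, which is an assumption. If they were not, it is one statement, three aligned sections and a check for the amendment.
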